12.1.3. Other Safety Assessments

Vital signs will be collected at each clinic visit (Screening, Baseline, Weeks 4, 6, 8, 12, 7 and 14 day Follow Up visits). It includes blood pressure, orthostatic blood pressure (after being supine for 5 minutes and 3 minutes after standing) pulse, height and weight.

Clinical Laboratory Assessments:

During the following clinic visit (Screening, Baseline, Week 12, 7-day and 14 day Follow Up visits), the following clinical laboratory tests will be performed. HbA1c will be measured at the baseline and completion/early termination visits.

Clinical Laboratory Tests					
Category	Parameters				
Hematology	Red blood cell count, hemoglobin, hematocrit, platelets, and white blood cell count with differential (neutrophils, bands lymphocytes, monocytes, eosinophils, basophils)				
Chemistry					
Electrolytes	Sodium, potassium, chloride, bicarbonate				
Liver function tests	Alkaline phosphatase, aspartate aminotransferase (AST), alanine aminotransferase (ALT), total bilirubin, direct bilirubin				
Renal function parameters	Blood urea/blood urea nitrogen (BUN), creatinine				
Other	Glucose, calcium, albumin, cholesterol, triglycerides, phosphorus, lactate dehydrogenase (LDH), total protein, globulin				
Pregnancy Test	Urine test (for women of childbearing potential only)				
Special Parameters	Hemoglobin A1c (HbA1c)				

Contraception Guidelines:

As specified in the Inclusion Criteria (Section 8.1), adolescent females of childbearing potential who are sexually active and male subjects who are sexually active must use a highly effective form of contraception throughout the study and for 30 days after the last dose of study drug. See the Contraception Guidelines for additional information.

Subjects must be monitored for signs of study drug abuse, and withdrawal or dependence and if detected must be recorded as AEs.

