13.2.2. Safety Analysis

All safety data will be summarized in Safety population according to the actual treatment.

Treatment-emergent adverse events (TEAEs) are defined as adverse events that are newly occurring or worsening after the first dose of study medication. The incidence of TEAEs will be summarized by treatment group, by severity and by relationship to study medication. Serious TEAEs and TEAEs leading to the study termination will be summarized by treatment group. Laboratory data, vital sign, physical examination and ECG will be summarized by treatment and visit.

The Columbia-Suicide Severity Rating Scale (C-SSRS), Abnormal Involuntary Movement Scale (AIMS), the Barnes Akathisia Rating Scale, the Swanson, Nolan and Pelham (SNAP-IV) questionnaire, the Children's Yale-Brown Obsessive Compulsive Scale (CY-BOCS), the Children's Depression Rating Scale-Revised (CDRS-R) and the Pediatric Anxiety Rating Scale (PARS) will also be summarized descriptively.

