10.5. Vital Signs

Vital sign measurements including sitting systolic blood pressure, sitting diastolic blood pressure, sitting pulse rate, supine orthostatic systolic blood pressure, supine orthostatic diastolic blood pressure, supine pulse rate, standing orthostatic systolic blood pressure, standing orthostatic blood pressure, and standing pulse rate at each scheduled time and changes from baseline in vital sign measurements will be summarized with descriptive statistics at each scheduled time point by treatment group.

Body height will be measured at Screening only and will be summarized by treatment group. Weight will be measured at each schedule visit and, along with changes from baseline, will be summarized with descriptive statistics at each scheduled time point by treatment group. Weight gain \geq 7% of body weight will be tabulated. Weight will be displayed in kilograms; height will be displayed in centimeters.

Body mass index (BMI) will be derived from the weight at each visit and from height (at screening), along with changes from baseline, will be summarized with descriptive statistics at each schedule timepoint by treatment group. BMI will be displayed in kilograms per meter squared.

All vital signs data will be presented in a listing.

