The condition power will then be calculated under the following for the treatment difference δ and standard error $Var(\hat{\delta}_1)$:

3) Using the estimates from the stage 1 data. Treatment difference δ is the Stage 1 MMRM treatment effect (δ₁) and Var(δ₁) is the variance of this estimate of treatment difference based on the covariance matrix of the LSmeans.

Using these results, the DSMB may make one of the following recommendations:

- If the conditional power at the planned sample size (150) is less than 30% then the DSMB may recommend that the study be terminated for futility.
- 2) If the conditional power at the planned sample size (150) is greater than 30% and less than 80%, then the planned sample size will be increased up to 200 to try to achieve a conditional power of at least 80%. If the conditional power at the maximum sample size (200) is still less than 80%, the DSMB may recommend continuing the study at the maximum sample size (200).
- If the conditional power is at least 80%, then the DSMB may recommend continuing this study with the planned sample size (150).

Full details of the DSMB including primary responsibilities, its relationship with other study components, its membership, and the purpose and timings of its meetings are documented in a DSMB charter. These details will also include procedures to ensure confidentiality and proper communication, the guidelines to be implemented by the DSMB and an outline of the content of the closed reports (unblinded) and open reports (blinded) that will be provided to the DSMB.

12. Changes from Analysis Planned in Protocol

There are no changes from the analysis planned in protocol.

13. Reference List

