Adverse Events	х	х	х	х	х	х	х	x	х	х	X*
Concomitant Medications	x	х		х	x	x		x	x	х	
Dispense Study Drug		Х		х	х	Х		Xf			
Collect Unused Study Drug/Assess drug compliance				x	x	x		x	x		

Abbreviations: AE = adverse event; BP = blood pressure; ECG = electrocardiogram; HR = heart rate; PK = pharmacokinetic(s)

^a Informed consent must be performed prior to any screening procedures. All screening procedures are to occur after washout of any applicable medications. Rescreening is allowed after approval by the Medical Advisor.

^b Vital signs will include, pulse, BP, orthostatic BP (done 5 minutes after being supine and then 3 minutes after standing), height and weight.

^c Subjects should be in a fasting state (8 hours) for laboratory tests. HbA1c will be measured at the baseline and completion/early termination visits.

^d Every attempt should be made to perform this assessment at the same time at each visit.

^e At Week 4 Study dose should not be taken until after pre-dose blood draw at the site. PK draws should be pre-dose, between 0.5 and 1.5 hours after study drug administration, and between 2 and 4 hours after study drug administration. Both Week 4 and Week 12, visits should be scheduled for the morning. At Week 12, blood sample will be collected in the afternoon at the end of the visit.

f Study drug will be dispensed for dose down titration.

- * Weeks 2 and 10 will be telephone visits. If there are any abnormal findings, the subject will be brought to the site for full assessment. A telephone call will be made to the subject 30 days after the last visit to assess any adverse events that may have occurred.
- ^g Assessments for these visits may be completed in locations other than study clinic and/or safety and efficacy assessments required at these visits will be made available for remote administration due to restrictions as a consequence of the COVID-19 pandemic or other qualifying event.
- ^h If visits at Weeks 4 and 12 are completed in locations other than study clinic due to restrictions as a consequence of the COVID-19 pandemic or other qualifying event, then collection of labs for PK assessments are optional

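### SAP 10.5 computes BMI at every visit from Screening height, against the scheduled height measurements, so within-arm BMI change is overstated in children who grow

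*SAP*

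**What the plan says.** SAP 10.5 makes two linked statements. On collection: "Body height will be measured at Screening only and will be summarized by treatment group". On derivation: "Body mass index (BMI) will be derived from the weight at each visit and from height (at screening"). BMI and its change from baseline are then summarised by treatment group at each scheduled time point.

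The schedule says otherwise in three places. Protocol 12.1.3 states "Vital signs will be collected at each clinic visit (Screening, Baseline, Weeks 4, 6, 8, 12, 7 and 14 day Follow Up visits"), and of those vital signs, "It includes blood pressure, orthostatic blood pressure (after being supine for 5 minutes and 3 minutes after standing) pulse, height and weight". Protocol Table 2 footnote b and footnote b of SAP Appendix 14.1 carry the same list: "Vital signs will include, pulse, BP, orthostatic BP (done 5 minutes after being supine and then 3 minutes after standing), height and weight". Both schedule tables mark vital signs at Screening, Baseline, Weeks 4, 6, 8 and 12, and at the 7- and 14-day follow-ups.

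On analysis, protocol 13.2.2 plans that "Laboratory data, vital sign, physical examination and ECG will be summarized by treatment and visit". SAP section 12 declares: "There are no changes from the analysis planned in protocol".

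**The concern.** The SAP contradicts both the protocol and its own appendix on when height is measured, and its BMI rule follows from the version that conflicts with the schedule. Subjects are aged 6 to under 18 and many will be growing. Screening may be up to 28 days before Baseline, so the height behind a Week 12 BMI can be 16 weeks old.

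The protocol names weight gain as an adverse event of special interest (12.2.1.3). A reader of the BMI table will want to know whether a rise within an arm is more than growth. BMI on current height helps with that question. BMI on a frozen height does not, because growth appears in the numerator as weight and never in the denominator. What is at stake is the correct reading of a descriptive safety table.

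**Working it through.** The documents give no BMI figure to reproduce. The check compares the SAP rule with BMI from same-visit height.

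**Inputs from the documents**
- BMI = weight (kg) / height (m)² (SAP 7.2).
- Height in the SAP rule: Screening only (SAP 10.5).
- Screening up to 28 days before Baseline; Week 12 is Day 84 (SAP 3.3, Appendix 14.1).
- Greatest nominal age of the height at Week 12: 28 + 84 = 112 days = 16 weeks.

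**Inputs assumed**: body sizes and growth rates, since the documents give neither.

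**Formulas.** Let W0 and W1 be weight at Baseline and Week 12, H0 and H1 the heights at those visits, and Hs the Screening height.
- SAP rule: change = W1/Hs² − W0/Hs² = (W1 − W0)/Hs²
- Same-visit height: change = W1/H1² − W0/H0²

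Under the SAP rule Hs² is constant for each child, so that child's BMI change is weight change rescaled.

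**Direction.** The SAP change exceeded the same-visit change in every growing case on a grid of Screening height 115, 140 and 165 cm, growth 1 to 10 cm a year, Screening gap 0 to 4 weeks, and weight change −60% to +30%.

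**Size without a growth rate.** Suppose a child grows 1 cm and true BMI is unchanged. The reported change is BMI0 × [((h + 1)/h)² − 1].
- 115 cm, 20 kg: BMI0 = 20/1.15² = 15.12; reported change 15.12 × [(116/115)² − 1] = +0.264 kg/m²
- 150 cm, 45 kg: BMI0 = 20.0; reported change 20.0 × [(151/150)² − 1] = +0.268 kg/m²

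**Size with assumed growth.** Twelve-week growth is the annual rate × 12/52. Hs is taken equal to H0. Changes are in kg/m².

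| Child | Assumed annual growth | 12-week height gain (cm) | 12-week weight gain (kg) | Change, SAP rule | Change, same-visit height | Overstatement |
|---|---|---|---|---|---|---|
| 115 cm, 20 kg | 5–7 cm, 2–3 kg | 1.15–1.62 | 0.46–0.69 | +0.35 to +0.52 | −0.08 to +0.21 | 0.31–0.43 |
| 150 cm, 45 kg | 5–8 cm, 4–6 kg | 1.15–1.85 | 0.92–1.38 | +0.41 to +0.62 | −0.08 to +0.30 | 0.31–0.50 |
| 175 cm, 90 kg | 0–2 cm, 0–3 kg | 0–0.46 | 0–0.69 | 0 to +0.23 | −0.15 to +0.23 | 0–0.16 |

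If Screening is placed 4 weeks before Baseline, the first row becomes 0.31 to 0.44, so the length of the gap matters little.

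**A single case.** Take 140 cm, 35 kg, 6 cm a year and a 2% weight gain. Weight rises 0.70 kg and height becomes 140 + 6 × 12/52 = 141.38 cm. The SAP rule gives 0.70/1.40² = +0.36. Same-visit height gives 35.7/1.4138² − 35/1.40² = 17.86 − 17.86 = 0.00. The whole reported change is an artefact.

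**The case against.** The strongest reply is that the trial is randomised 1:1 against placebo and stratified by weight band. Expected growth is shared by the arms, and SAP 10.5 already reports weight, weight change and gain of at least 7% by treatment group. Drug-related excess gain is read from that contrast. This stands, and it limits the point to the within-arm BMI summaries. BMI enters no test or stopping rule, and dose is fixed on Baseline weight. SAP 4.1.1 lists the absence of dose adjustment for BMI change as an intercurrent event, but handles it by treatment policy, so the derived BMI value does not enter the primary analysis.

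It can also be said that the protocol plans no BMI analysis. That is correct: the departure from protocol 13.2.2 is only that height is not summarised by visit. And the SAP may describe what was actually collected; no case report form is available to settle this.

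Several stronger readings are tempting, and the documents do not support them.
- **That the BMI table adds nothing to the weight table.** The divisor is constant within a child but differs between children, so a group mean BMI change is not a rescaled group mean weight change.
- **That every child aged 6 to under 18 with stable BMI is misreported.** Only those who grew are.
- **That the programme shows a paediatric weight signal which this rule hides.** Protocol 5.3.1 does report that almost all children in the open-label extension gained weight, but that study had no control arm. In the controlled paediatric study, protocol 5.2.2.1 reports no evidence of an effect on weight, and protocol 5.3.1 gives gains of 5 pounds or more in 17.5% on ecopipam against 15% on placebo.
- **That counting weight gain of 7% but not loss is a second defect.** The protocol names only gain as of special interest. Loss remains visible in the weight-change summaries (which include the minimum), the listings and the adverse event tables.

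**Conclusion.** The concern holds as a minor correction. SAP 10.5 conflicts with protocol 12.1.3, protocol Table 2 footnote b and SAP Appendix 14.1 footnote b, and its BMI rule overstates within-arm BMI change in children who grow. The overstatement is about 0.26 kg/m² per centimetre of growth at unchanged BMI in the two sizes worked. Over 12 weeks it is about 0.3 to 0.5 kg/m² if growth is 5 to 8 cm a year, and nil without growth. The growth rates and body sizes are assumptions. The age and size mix of the trial is not given, so no trial-level figure can be stated.

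A reader might infer that the comparison of ecopipam with placebo is biased. It is not materially so unless the drug itself alters growth, and efficacy is untouched. The textual conflict is certain; whether the remedy is available depends on height having been recorded as scheduled.

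**What to change.** In SAP 10.5:
1. Remove the restriction of height measurement to Screening.
2. Summarise height by treatment and visit.
3. Derive BMI from weight and height measured at the same visit, with Baseline BMI from Baseline height, and do not carry Screening height forward.
4. Show the number of subjects with both measurements at each visit.

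If height was not recorded after Screening, drop the change-in-BMI summary and record in SAP section 12 that height was not collected and summarised as the protocol planned.

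If the data exist, the cost is SAP wording and programming only. There are two downsides. Visits held remotely, which both schedules allow, may lack height, so BMI will be available for fewer subjects. Height error also enters the result: an assumed 0.5 cm error moves BMI by about 0.13 kg/m² at 115 cm and 20 kg. That matters most at early visits. By Week 4, assumed growth of 5 to 7 cm a year is only 5 × 4/52 = 0.38 to 7 × 4/52 = 0.54 cm, about the size of that error. By Week 12 the same rates give 1.15 to 1.62 cm, and current height is clearly the better choice.

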10.6. ECG

The following ECG data will be collected at the Screening, Baseline, Week 4, Week 6, Week 8, Week 12, 7 Day Follow Up and 14 day Follow Up visits:

- PR interval (msec)
- QRS interval (msec)
- QT interval

- QTc interval (msec)
- Overall ECG result (Normal; Abnormal, Not Clinically Significant; Abnormal, Clinically Significant).

An ECG is optional at unscheduled visits, per the investigator's discretion.

The actual ECG results along with change from baseline will be summarized at each visit by treatment group. All ECG data will be presented in a listing.

10.7. Physical Examination

A Physical examination will be performed at the Screening, Baseline, Week 4, Week 6, Week 8, Week 12, 7 Day Follow Up and 14 day Follow Up visits. This will include physical examination of the following body areas and systems: Head, Eyes, Ears, Nose, Mouth, Throat, Neck (including Thyroid); Thorax; Abdomen; Urogenital; Extremities; Neurological; Skin and Mucosae; and Other.

A physical exam is optional at unscheduled visits, per the investigator's discretion.

The Physical examination results will be summarized at each visit by treatment group. All physical examination data will be presented in a listing.

10.8. Columbia Suicide Severity Rating Scale (C-SSRS)

The C-SSRS is a low burden (approximately 5 minutes for completion) instrument to assess both suicidal behavior and ideation. The scale is appropriate for subjects from age 6 through to an elderly population.

The number and percentage of subjects with suicidal behavior and ideation will be summarized by treatment group at the Baseline, Week 4, Week 6, Week 8 and Week 12 visits and all questionnaire data will be displayed in a listing.

10.9. Other Safety

10.9.1. Abnormal Involuntary Movement Scale (AIMS)

Abnormal Involuntary Movement Scale (AIMS) records the occurrences of tardive dyskinesia (TD) in subjects receiving neuroleptic medications. The test is used to detect TD and to follow the severity over time. It consists of rating the presence and severity of movement disorders involving the face, mouth, extremities, and trunk as well as three items of global judgment from a scale of 0 (none) to 4 (severe).

The AIMS total score will by calculated by summing the severity of the 10 items that are rated on a scale of 0 to 4. The total score will be summarized by treatment group at the Baseline, Week 4, Week 6, Week 8 and Week 12 visits and all questionnaire data will be displayed in a listing.

10.9.2. Barnes Akathisia Rating Scale (BARS)

The Barnes Akathisia Rating Scale (BARS) is used to assess the severity of drug-induced akathisia. Objective and subjective items in the scale measure the level of subject's restlessness, ranging from zero (normal) to 3 (most severe). The BARS also includes a global assessment of akathisia, ranging from zero (absent) to 5 (severe).

The objective, subjective, and global scores will be summarized by treatment group at the Baseline, Week 4, Week 6, Week 8 and Week 12 visits and all questionnaire data will be displayed in a listing.

10.9.3. Swanson, Nolan and Pelham (SNAP-IV) questionnaire

Swanson, Nolan and Pelham (SNAP-IV) questionnaire measure designed assess ADHD and oppositional defiant disorder (ODD) symptoms in children and adolescents. The SNAP-IV is based on a 0 to 3 rating scale: Not at AII = 0, Just A Little = 1, Quite A Bit = 2, and Very Much = 3. Subscale scores on the SNAP-IV are calculated by summing the scores on the items in the subset and dividing by the number of items in the subset. The score for any subset is expressed as the Average Rating-Per-Item.

The items from the DSM-IV (1994) criteria for Attention-Deficit/Hyperactivity Disorder (ADHD) are included for the two subsets of symptoms: inattention (items #1-#9) and hyperactivity/impulsivity (items #11-#19). Also, items are included from the DSM-IV criteria for Oppositional Defiant Disorder (ODD, items #21-#28) since it often is present in children with ADHD.

In addition to the DSM-IV items for ADHD and ODD, the SNAP-IV contains items from the Conners Index Questionnaire (Conners, 1968) and the IOWA Conners Questionnaire (Loney and Milich, 1985). The IOWA was developed using divergent validity to separate items which measure inattention/overactivity (I/O — items #4, #8, #11, #31, #32) from those items which measure aggression/defiance (A/D — items #21, #23, #29, #34, #35). The Conners Index (items #4, #8, #11, #21, #32, #33, #36, #37, #38, #39) was developed by selecting the items which loaded highest on the multiple factors of the Conners Questionnaire, and thus represents a general index of childhood problems.

The SNAP-IV also includes the 10 items of the Swanson, Kotkin, Agler, MyInn, and Pelham (SKAMP) Rating Scale. These items are classroom manifestations of inattention, hyperactivity, and impulsivity (i.e., getting started, staying on task, interactions with others, completing work, and shifting activities). The subscales of the SKAMP include academic (items #81-86) and deportment (items #87-90).

The subscale scores will be summarized by treatment group at the Baseline, Week 4, Week 6, Week 8 and Week 12 visits and all questionnaire data will be displayed in a listing.

10.9.4. Children's Yale-Brown Obsessive Compulsive Scale (CY-BOCS)

Children's Yale-Brown Obsessive Compulsive Scale (CY-BOCS) is a reliable and valid scale to both determine severity of OCD and to monitor improvement during treatment. The scale is a clinician-rated, 10item scale that includes questions about the amount of time spent on obsessions/compulsions, level of impairment or distress, and how much resistance and control subjects have over these thoughts.

Severity of compulsions and obsessions are rated on a five-point scale from 0 to 4. CY BOCS total score is computed as the sum of the 10 items, ranging from 0 to 40, with higher scores indicating more severe compulsions and obsessions.

The total score will be summarized by treatment group at the Baseline, Week 4, Week 6, Week 8 and Week 12 visits and all questionnaire data will be displayed in a listing.

10.9.5. Children's Depression Rating Scale-Revised (CDRS-R)

Children's Depression Rating Scale-Revised (CDRS-R) is a clinically validated rating scale designed to assess psychiatric signs and symptoms of depressions. Fourteen signs and symptoms are rated from 1 (normal) to 7 (most severe), and 3 signs and symptoms are rated from 1 (normal) to 5 (most severe). The raw summary score is the sum of all 17 items, ranging from 17 to 113.

The raw summary score will be summarized by treatment group at the Baseline, Week 4, Week 6, Week 8 and Week 12 visits and all questionnaire data will be displayed in a listing.

